4.3.2. Supportive Secondary Endpoint(s)

OS rate at 12, 24 and 36 months

The non-parametric Kaplan-Meier method will be used to estimate the survival curves. OS rate at 12 months, 24 months and 36 months, and the corresponding 95% CI will be estimated from the Kaplan-Meier analysis will be reported separately for the total and PD-L1 CPS ≥ 1 populations. The confidence intervals will be based on the Brookmeyer-Crowley method (1982).

If no participants have follow-up duration exceeding the OS milestone, the corresponding summary will not be produced.

A supportive summary of the duration of follow-up will also be produced, presenting the minimum, maximum, median and 25th and 75th percentiles.

Objective Response Rate (ORR) and Disease Control Rate (DCR) per RECIST v1.1

Best Overall Response (BOR)

- The best overall response is the best response recorded from the date of randomization until disease progression or initiation of new anti-cancer therapy, whichever is earlier, as assessed by the investigator per RECIST v1.1. The order from best to worst of the available responses is CR, PR, stable disease (SD), progressive disease (PD) and not evaluable (NE).
- As a randomized double-blind study in which primary endpoints are OS and PFS, the confirmation of CR and PR is not required.
- A subject without any adequate post-baseline assessments will have a BOR of NE.
- To be assigned a status of SD as the best overall response, the minimum criteria for SD duration must be met. Since disease assessment starts at week 9 and a window of ± 7 days is allowed, 56 days since the date of randomization will be used as the minimum criteria for SD duration.

ORR per RECIST v1.1 is defined as the proportion of the participants who have a complete response (CR) or partial response (PR) as the best overall response per RECIST v1.1 based upon investigator assessment.

DCR per RECIST v1.1 is defined as the percentage of participants with a best overall response of CR or PR at any time plus the percentage of participants with SD meeting the minimum time of 15 weeks per RECIST v1.1 based upon investigator assessment. A status of $SD \geq 15$ weeks will be assigned if the follow-up disease assessment has met the SD criteria at least once after the date of randomization at a minimum of 14 weeks (98 days) considering a one-week visit window.

The number and percentage of participants achieving BOR of CR, PR, SD, PD, NE, as well as those meeting SD durability requirements ($SD \geq 15$ weeks) will be provided separately for the PD-L1 total and $CPS \geq 1$ participants.

The number and percentage of participants achieving ORR and DCR per RECIST v1.1 will be provided separately for the PD-L1 total and $CPS \geq 1$ participants. The 2-sided 95% exact (Clopper-Pearson) confidence limits for the binomial proportion will also be included.

Stratified Miettinen and Nurminen's method will be used for comparison of the ORR/DCR between two treatment groups. The difference in ORR/DCR and its 95% confidence interval from the stratified Miettinen and Nurminen's method with strata weighting by sample size [Chow, 2003] (i.e. where larger strata carry more weight as compared to smaller strata) with a single treatment covariate will be reported separately for the PD-L1 total and $CPS \geq 1$ participants. Participants with unknown or missing response will be treated as non-responders that is these participants will be included in the denominator when calculating the percentage of ORR/DCR.

Duration of Response (DoR) per RECIST v1.1

Duration of response (DoR) per RECIST v1.1 is defined as the time from first documented evidence of CR or PR until first documented disease progression per RECIST v1.1 based upon investigator assessment or death due to any cause, whichever occurs first, among participants who demonstrated CR or PR as the best overall response per RECIST v1.1. Censoring rule will follow those for the primary analysis of PFS per RECIST v1.1.

If the number of participants with a best overall response of CR or PR permits, the Kaplan-Meier method will be used to estimate the survival curves for DoR per RECIST v1.1. The Kaplan-Meier estimates for the median DoR and the first and third quartiles, along with 95% CIs estimated using the [Brookmeyer-Crowley](#) method (1982) will be reported separately for the PD-L1 total and CPS ≥ 1 group by study intervention.

Adverse Events/Serious Adverse Events

The safety analyses will be based on the safety analysis set, unless otherwise specified.

Adverse events analyses including the analysis of adverse events (AEs), Serious AEs (SAEs) and other significant AEs will be based on GSK Core Data Standards.

An overview summary of AEs, including but not limited to, counts and percentages of participants with any AE, AEs related to study intervention, Grade 3+ AEs, Grade 3+ AEs related to study intervention, AEs leading to permanent discontinuation of study intervention, study intervention related AEs leading to permanent discontinuation of study intervention, AEs leading to dose delays, SAEs, SAEs related to study intervention, fatal SAEs, fatal SAEs related to study intervention and AESIs will be produced.

Adverse events will be coded using the standard Medical Dictionary for Regulatory Affairs (the latest MedDRA dictionary version at the time of reporting) and graded by the investigator according to the NCI-CTCAE v5.0 [[NCI, 2017](#)].

A summary of number and percentage of participants with any adverse events by maximum grade will be produced. AEs will be sorted by System Organ Class (SOC) and Preferred term (PT) in descending order. The summary will use the following algorithms for counting the participant:

- **Preferred term row:** Participants experiencing the same AE preferred term several times with different grades will only be counted once with the maximum grade.
- **Any event row:** Each participant with at least one adverse event will be counted only once at the maximum grade no matter how many events they have.

The frequency and percentage of AEs (all grades) will also be summarized and displayed in descending order by PT only.

A separate summary will be provided for study intervention-related AEs by PT and maximum grade. A study intervention-related AE is defined as an AE for which the investigator classifies the possible relationship to study intervention as “Yes”. A worst-case scenario approach will be taken to handle missing relatedness data, i.e. the summary table will include events with the relationship to study intervention as ‘Yes’ or missing.

All SAEs will be tabulated based on the number and percentage of participants who experienced the event by SOC and PT. A separate summary will also be provided for study intervention-related (fatal and non-fatal) SAEs. The summary tables will be displayed by PT.

A study intervention-related SAE is defined as an SAE for which the investigator classifies the relationship to study intervention as “Yes”. A worst-case scenario approach will be taken to handle missing data, i.e. the summary table will include events with the relationship to study intervention as ‘Yes’ or missing.

A summary of fatal AEs by PT will also be produced.

A summary of non-serious AEs that occurred in strictly 5% of the participants or above will be provided (no rounding for the percentage will be used in terms of 5% threshold, e.g., event with 4.9% incidence rate should not be included in this table). The summary will be displayed by System Organ Class (SOC) and Preferred Term (PT) in descending order of total incidence.

All AEs will be listed. Additionally, a listing of subject IDs for each individual AE will be produced.

Adverse Events of Special Interest (AESI)

The summary of event characteristics will be provided for each AESI (refer to protocol for details) respectively, including number of participants with any event, number of events, number of participants with any event that is serious, number of participants with any event that is related to study intervention, number of occurrences (one, two, three or more), maximum grade, outcomes and the action taken for the event.

The percentage will be calculated in two ways, one with number of participants with event as the denominator and the other with total number of participants as the denominator.

The worst-case approach will be applied at participant level for the maximum grade, i.e. a participant will only be counted once as the worst-case from all the events experienced by the participant.

For action taken to an event, a participant will be counted once under each action. Summary statistics showing the time to onset and the duration of the first occurrence for AESI may also be presented as appropriate.

Dose Modifications

The summaries of dose modifications (dose interruptions, missed doses and dose delays) will be provided if the data warrant. All the dose interruptions, missed doses and dose delays will be listed separately if data warrant.

Dose interruptions will be summarized by number of interruptions and reasons for interruption.

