No baseline disease assessments and the participant has not died	Censored at the date of randomization
No post-baseline disease assessments and the participant has not died	Censored at the date of randomization
With post-baseline disease assessments, new anticancer treatment is not initiated and no documented PD or death	Censored at the date of last adequate radiological disease assessment ¹
With post-baseline disease assessments and new anticancer treatment is initiated (prior to documented PD or death) ²	Censored at the date of last adequate radiological disease assessment on or prior to the initiation of new anticancer treatment
PD or death documented after ≤ 1 missed disease assessment	Progressed at the date of documented PD ³ or death
PD or death documented after ≥ 2 missed disease assessments	Censored at the date of last adequate radiological disease assessment prior to the ≥ 2 missed disease assessment

Abbreviations: CR=complete response; PD=progressive disease; PFS=progression-free survival; PR=partial response; RECIST=response evaluation criteria in solid tumors; SD=stable disease

1. An adequate assessment is defined as an assessment where the investigator assessed response is CR, PR, or SD.
2. If PD and new anti-cancer therapy occur on the same day, it is assumed that the progression was documented first (i.e. outcome is progression; the date is the date of the assessment for progression).
3. The earliest of (i) Date of radiological assessment showing new lesion (if progression is based on new lesion); or (ii) Date of radiological assessment showing unequivocal progression in non-target lesions, or (iii) Date of last radiological assessment of measured lesions (if progression is based on increase in sum of measured lesions).

The non-parametric Kaplan-Meier method will be used to estimate the PFS curves. The treatment difference in PFS will be assessed by the stratified log-rank test. A stratified Cox proportional hazard model with Efron's method of tie handling will be used to assess the magnitude of the treatment difference (i.e., hazard ratio) between the treatment arms. The hazard ratio and its 95% confidence interval from the stratified Cox model with Efron's method of tie handling and with a single treatment covariate will be reported.

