4.2. Primary Endpoint(s) Analysis

4.2.1. Definition of Endpoint(s)

Overall Survival (OS)

Overall Survival (OS) is defined as the interval of time from the date of randomization to the date of death due to any cause.

Participants without documented death will be censored at last known alive date. The last date will be determined by the maximum collection/assessment date from among selected data domains within the clinical database; details will be provided in a separate Output and Programming Specification (OPS) document.

Progression-Free-Survival (PFS) per RECIST v1.1

Progression-free-survival (PFS) per RECIST v1.1 by investigator assessment is defined as the time from the date of randomization to the date of the first objectively documented disease progression per RECIST v1.1 based on investigator assessment, or death due to any cause, whichever occurs first.

The date of disease progression is defined as the date of radiological disease progression based on imaging data per RECIST v1.1. For cases where symptomatic progression is documented by the investigator, the derived response based on tumor assessment data will be utilized.

For participants who receive subsequent anticancer therapy, the following rules will apply:

- If a participant has only a baseline visit or does not have an adequate post-baseline radiological assessment on or prior to the date of initiation of anticancer therapy, PFS will be censored at the date of randomization.
- If anticancer therapy is started without documented disease progression or is started prior to documented disease progression, then PFS will be censored at the date of the last adequate radiological assessment on or prior to the initiation of anticancer therapy (i.e., if an assessment occurs on the same day as the start of new anticancer therapy, the assessment will be used as it is assumed that the assessment occurred prior to the administration of new anticancer therapy). The date of the last adequate radiological assessment will be used as the censoring date.

- If the start date of anticancer therapy is partial, the imputation rules described in the OPS will be applied.

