Since PFS is interval censored, extended loss to follow-up prior to PD or death increases the uncertainty when the event occurs. As such, PFS will be analyzed censoring for extended time without an adequate assessment to account for missed response assessments prior to disease progression or death. Specifically, if there are two or more assessments which are missing followed by an assessment of PD or death, PFS will be censored at the last adequate assessment prior to PD or death.

A summary of the assignments for progression and censoring dates for the primary analysis of PFS per RECIST v1.1 is also illustrated in [Table 3](#).

Table 3 Censoring Rules for Primary Analysis of PFS per RECIST v1.1

Situation	Primary Analysis
No or incomplete baseline disease assessments and the participant has not died	Censored at the date of randomization
No adequate ¹ post-baseline disease assessments (prior to anticancer therapy, if initiated) and the participant has not died ²	Censored at the date of randomization
With adequate post-baseline disease assessments, new anticancer treatment is not initiated, and no documented PD or death	Censored at the date of last adequate radiological disease assessment
With adequate post-baseline disease assessments before the start of new anticancer therapy, and new anticancer treatment is initiated (prior to documented PD or death) ³	Censored at the date of last adequate radiological disease assessment on or prior to starting new anticancer treatment
PD or death documented after ≤ 1 missed disease assessment ⁴	Progressed at the date of documented PD ⁵ or death, whichever occurs first
PD or death documented after ≥ 2 missed disease assessments ^{4,6}	Censored at the date of last adequate radiological disease assessment prior to the ≥ 2 missed disease assessment ⁷

Abbreviations: CR=complete response; PD=progressive disease; PFS=progression-free survival; PR=partial response; RECIST=response evaluation criteria in solid tumors; SD=stable disease

1. An adequate assessment is defined as an assessment where the investigator assessed response is CR, PR, or SD
2. In case participant has documented PD but no other adequate assessments, see scenarios below.
3. If PD and new anti-cancer therapy occur on the same day, it is assumed that the progression was documented first (i.e., outcome is progression; the date is the date of the assessment for progression).

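### The SAP's definition of an adequate assessment leaves out PD, so one best-overall-response rule and one PFS censoring rule contradict the rest of the SAP for participants whose only post-baseline response is PD

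*SAP*

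**What the plan says.** **Definition.** Footnote 1 to SAP Table 3 (section 4.2.1) reads "An adequate assessment is defined as an assessment where the investigator assessed response is CR, PR, or SD". Protocol Table 10, footnote 1 defines the term in the same way. The SAP has no other definition.

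**Best overall response (SAP 4.3.2).** Bullet 1 takes the best response recorded up to progression or new therapy and ranks the categories CR, PR, SD, PD, NE. Bullet 3 says "A subject without any adequate post-baseline assessments will have a BOR of NE". The last bullet says "56 days since the date of randomization will be used as the minimum criteria for SD duration". The section then plans counts of CR, PR, SD, PD and NE, each as its own row.

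**PFS (SAP 4.2.1).** A list of rules opens with "For participants who receive subsequent anticancer therapy, the following rules will apply". Under its first bullet, a participant who "does not have an adequate post-baseline radiological assessment on or prior to the date of initiation of anticancer therapy, PFS will be censored" at randomization. The second bullet is limited to therapy started without, or before, documented progression. In Table 3, the row for no adequate post-baseline assessment carries footnote 2: "In case participant has documented PD but no other adequate assessments, see scenarios below". The matching row of protocol Table 10 has no such qualifier: "No post-baseline disease assessments and the participant has not died".

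**The concern.** Leaving PD out of the definition makes sense where the term picks the last progression-free scan as a censoring date. It does not make sense in a rule that decides whether a participant has any usable post-baseline information, because a scan showing PD is usable information.

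Two outputs are at stake. The best-response table could show the clearest treatment failures as not evaluable, so that PD is understated and NE overstated. For PFS, a primary endpoint still reported in the main CSR, an event could be replaced by zero follow-up for a participant who progresses at the first scan and then starts new therapy.

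Little in the plan would expose such a slip. Sensitivity and supplementary analyses are dropped (SAP 4.2.3, 4.2.4) and no central review will be done (SAP 4.6.1). If both rules were programmed literally, the participant would be NE in one table and censored at day 0 in the other. The two outputs would agree with each other.

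**Working it through.** **1. The plan's own figure, as a check on inputs.** Protocol 9.2.1 states 93.1% PFS power with 470 events, HR 0.62 and one-sided alpha 0.01%. By Schoenfeld's formula, z = (√470 / 2) × |ln 0.62| − 3.719 = 10.84 × 0.478 − 3.719 = 1.46, which is 92.8%. The figure reproduces. The point itself rests on wording, not on this number.

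**2. Best overall response, rule by rule.** Bullet 1 and bullet 3 (with the footnote definition) applied to the same sequences, taking SD at day 56 or later:

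| Post-baseline responses | Bullet 1 | Bullet 3 |
|---|---|---|
| none | NE | NE |
| NE only | NE | NE |
| PD only | **PD** | **NE** |
| SD, then PD | SD | SD |
| PR, then PD | PR | PR |

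Only the PD-only participant gets two answers. The first scan is at Week 9 ± 7 days, so no earlier than day 56, and SD on a scheduled scan always meets the 56-day minimum. Nearly everyone whose best response is PD therefore had PD with no earlier CR, PR or SD. Bullet 3 read literally would leave the PD row almost empty.

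**3. How many participants.** Inputs from protocol 9.2.1: control PFS exponential with median 5 months, PFS HR 0.62, control OS 77% at 6 months, OS HR 0.72. Assumptions added here: constant hazards, the OS hazard ratio acting from randomization, first scan at day 63 (63 / 30.4375 = 2.07 months), and first-scan PD approximated as PFS events minus deaths by that day.

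- Control PFS events: 1 − exp(−ln 2 × 2.07 / 5) = 24.9%. Deaths: 1 − 0.77^(2.07/6) = 8.6%. Difference: about 16%.
- Experimental PFS events: 1 − exp(−0.62 × ln 2 × 2.07 / 5) = 16.3%. Deaths: 1 − 0.77^(0.72 × 2.07/6) = 6.3%. Difference: about 10%.
- With the scan at day 56, the differences are 22.5 − 7.7 = 14.8% and 14.6 − 5.6 = 9.0%. At day 70 they are 27.3 − 9.5 = 17.8% and 17.9 − 7.0 = 10.9%.

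**4. PFS, one participant through each rule.** Take PD at Week 9, no earlier response, and new therapy at Week 12.

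- SAP 4.2.1, first new-therapy bullet: no CR, PR or SD on or before therapy, so censored at randomization.
- SAP 4.2.1, second bullet: does not apply, because therapy followed documented PD.
- SAP Table 3, row for no adequate post-baseline assessment: footnote 2 sends this case to the rows below.
- SAP Table 3, new-therapy row: does not apply, because therapy did not precede PD.
- SAP Table 3, row for PD after at most one missed assessment: event at the PD date.
- Protocol Table 10: the participant has a post-baseline assessment, so the no-assessment row does not apply; event at the PD date.

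One sentence of text says censor. Both tables say event. The fraction of first-scan progressors who start new therapy is not in the documents, so no number can be put on the PFS side.

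**The case against.** The strongest reply is that the intent is plain. The definition is a footnote to a PFS censoring table, and 4.3.2 does not cite it. Bullet 1 ranks PD above NE, and a planned PD row that would be nearly empty cannot have been meant. For PFS, the table handles this exact case through footnote 2, its new-therapy row applies only before documented PD, and the endpoint is defined by first documented progression. On that view, a competent programmer would get both right.

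Most of this stands. A reader might infer that the SAP settles on NE for first-scan progressors, or that it deletes their PFS events. The documents do not support either: each rule is opposed by other text that points to the right answer.

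A reader might also infer a large loss of PFS information. Counting every event by day 63 as lost would give 320 × (0.249 + 0.163), or about 132 events. That is not an estimate. It includes deaths and participants who never start new therapy, and it presumes a 640-participant, 470-event analysis that early termination has ruled out. Amendment 2 also took follow-up of subsequent therapy out of the Schedule of Activities, which may reduce the number caught.

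The consequences are limited too. PD and NE both count as non-response, so ORR and DCR do not move. DoR covers responders only. Best overall response is not itself a listed endpoint.

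What does not stand is that the text can be left alone. The term is defined once, the best-response bullet uses it without restating it, and the first new-therapy bullet lacks the exception that the second one has.

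**Conclusion.** Two internal contradictions, both caused by using a definition without PD where PD should count. Both have a clear intended answer: a best overall response of PD, and a PFS event at the PD date.

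For best overall response, the literal rule would move most first-scan progressors from PD to NE: very roughly 16% of control and 10% of experimental participants. These figures rest on the design's PFS and OS assumptions, constant hazards, and a first scan near Week 9. They are not predictions for the terminated trial.

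For PFS, the conflict is confined to participants who start new therapy after PD at the first scan, and its size is unknown. ORR, DCR and DoR are unaffected. This is a correction of wording, worth making because the best-response table and PFS are both still to be reported.

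**What to change.** - SAP 4.3.2, bullet 3, replace with: *A participant with no post-baseline assessment of CR, PR, SD or PD will have a BOR of NE.*
- SAP 4.2.1, first bullet for participants who receive subsequent therapy, add after the condition on adequate assessments: *and has no documented PD on or prior to the start of anticancer therapy*. The text then agrees with Table 3 footnote 2 and protocol Table 10.

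The definition in Table 3 footnote 1 can stay, since it serves the censoring dates correctly. The cost is two sentences of SAP text and a check that the programming specification follows them. No new data are needed.
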